8.4.1. Adverse Events

Adverse events will be coded MedDRA Version 25.1 Intensity/severity and relationship of AE will be evaluated by the investigator.

A TEAE will be assessed among HD patients and is defined as an AE with onset on or after the first dose of IP, or any worsening of a pre-existing medical condition/AE with onset after the start of IP and throughout the study. The analysis of AEs will be based on the concept of

TEAEs. Where the AE start date is missing, adverse events will be assumed to be treatment-emergent, unless there is clear evidence (through comparison of partial dates) to suggest that the adverse event started prior to the first dose of study treatment. Missing or partial dates will be imputed for AE. The algorithm for missing or partial start/end date is documented in [Appendix D](#).

Adverse events are assigned an AE period based on the onset date/time. AE periods are defined as follows:

- Pre-treatment AE: AE onset date before first IP dosing date/time
- TEAE: AE onset date/time on or after the first IP dose date/time (If an AE start date same as IP first dose date, but no time either in AE start or treatment start, then consider this AE to be in treatment period TEAE)
- On-treatment TEAE: AE onset date/time on or after first IP dose date/time and on or before IP last dose date + 30 days (Note that time does not matter for the end of this period. i.e. if AE occurred after the last dose but on the same date of last dose, it is considered as on-treatment TEAE)
- Post-treatment TEAE: AE onset date on or after IP last dose date + 31 days. An overall summary of TEAEs will include the number and percentage of participants and number of events in the following categories: Any TEAEs
- Any TEAEs (On-treatment, Post-treatment)
- TEAEs by maximum Severity (severe>moderate>mild)
- Any related TEAEs
- Any related TEAEs by maximum Severity (severe>moderate>mild)
- Any serious TEAEs
- Any serious related TEAEs
- Any TEAEs leading to death
- Any TEAEs leading to IP withdrawal
- Any TEAEs leading to withdrawal from the study
- Any TEAEs leading to IP interruption

Incidence of TEAEs in following categories will be provided by SOC and PT. A participant is counted only once under each SOC and PT in case of multiple occurrences of the same AE. These tables will be sorted by decreasing frequency of System Organ Class (SOC) in SAGE-718 group, then in placebo group, then alphabetically first within SOC then within preferred term.

- TEAE

- On-treatment TEAE
- Post-treatment TEAE
- TEAEs by maximum Severity
- TEAEs by relationship
- Serious TEAEs
- TEAEs leading to IP withdrawal
- TEAEs leading to withdrawal from the study
- TEAEs leading to IP interruption

Additionally, incidence of TEAEs will be summarized by PT. Most common TEAEs reported >5% in either treatment group will also be summarized by PT.

For maximum severity, participants will be counted only once within each SOC and PT at the maximum severity in the following order: severe > moderate > mild; an AE with missing severity will be omitted from severity presentation and will not be imputed. For relationship to IP, participant will be counted only once within each SOC and PT at the strongest relationship to IP in the following order: related > not related; an AE with relationship missing is treated as related. For seriousness, an AE with missing seriousness will not be imputed. The incidences will be presented by descending frequency of SOC and then, within a SOC, by descending frequency of PT based on the participant count, and in alphabetical order of PT if the incidence within a PT is a tie.

In addition, TEAE summary by SOC/PT will also be presented by the following subgroups:

- Race (Black or African American, White, Other)
- Sex (Male, Female, Unknown/Undifferentiated)
- BMI (≤ 18.4 , $18.5-24.9$, $25-29.9$, ≥ 30 kg/m²)
- Country (US, Rest of World)
- Age group: ≤ 50 , > 50 years

A by-participant listing of all AEs, SAEs (including those with onset or worsening before the start of IP), TEAEs leading to death, TEAEs leading to IP withdrawal through the end of the study, TEAEs leading to withdrawal from the study, and most frequent (5%) TEAEs will be provided.

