5.2. Sample Size and Power

The study is designed to detect a difference between participants with HD and HP on HD-CAB composite score as the primary endpoint. Using a two-sided alpha level of 0.05, a sample size of at least 80 participants (40 HP and 40 participants with HD) would provide at least 80% power to detect a baseline difference in HD-CAB composite score assuming Cohen's D effect size equal to 0.63, which is in the range of effect sizes reported in the literature (Stout et al., 2014).

Using a CI approach for sample size estimation, and assuming a common SD of 1.51 in HD-CAB, a sample size of 32 evaluable participants with HD (16 per treatment arm) will provide 80% confidence level for estimating the population mean with 0.50 precision or margin of error.

Assuming a 20% dropout rate in participants with HD, a sample size of approximately 40 participants with HD will be randomized in a 1:1 ratio to SAGE-718 and placebo to obtain 32 evaluable participants with HD. Additional participants may be randomized if the dropout rate is higher than 20%.

Evaluable participants with HD are defined as those randomized participants who receive IP and have a valid baseline and at least 1 postbaseline efficacy assessment.

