8. STATISTICAL ANALYSIS

8.1. General Considerations

Continuous data will be summarized in terms of the number of participants, mean, standard deviation (SD), minimum, and maximum. The minimum and maximum will be reported to the same number of decimal places as the raw data recorded in the database. The mean and median will be reported to one more decimal place, and the SD (and the standard error [SE], if applicable) will be reported to two more decimal places, than the raw data recorded in the database. In general, the maximum number of decimal places reported shall be four for any summary statistic. Any values that require transformation to standard units (metric or SI) will be converted with the appropriate corresponding precision.

Categorical data will be summarized in terms of the number of participants providing data at the relevant time point (n), frequency counts, and percentages. Percentages will be reported to one decimal place unless otherwise specified. Any planned collapsing of categories will be detailed in the SAP text and the data displays.

Percentages will not be presented for zero counts. Percentages will be calculated using the number of participants (n) as the denominator. A missing category shall be included only for categorical variables where no data is available. The missing category will be omitted if there are no missing values for that variable.

For the laboratory results that are “ $\leq x$ ” or “ $\geq x$ ”, where x is a number as collected in the data, the numeric part of the result will be used in the calculation in the summary tables. If a laboratory value contains ‘y <’ then y minus 0.1 for values measured to the first decimal place, 0.01 for values measured to the second place, 0.001 for values measured to the third decimal place, and so on, will be used for the analysis. If a laboratory value contains ‘z >’ then z plus 0.1 for values measured to the first decimal place, 0.01 for values measured to the second place, 0.001 for values measured to the third decimal place, and so on, will be used for the analysis. The same is true if the result is presented as below limit of quantification (BLQ) and a lower limit of quantification (LLOQ) value is provided – LLOQ value will be used for calculation in the summary tables. The actual results as collected will be displayed in the listings.

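### Two display rules in SAP 8.4.1 can distort the severity and most-common TEAE tables, without changing any TEAE incidence: ungraded events are left out of severity, and the 5% cut-off steps from one participant to two at the planned arm size

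*SAP*

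**What the plan says.** **Missing attributes.** SAP 8.4.1 counts each participant once per SOC and PT at maximum severity and adds that "an AE with missing severity will be omitted from severity presentation and will not be imputed". For causality the rule goes the other way: "an AE with relationship missing is treated as related". An AE with no start date is assumed treatment-emergent unless partial dates show otherwise. Missing seriousness is not imputed. On missing categories in general, SAP 8.1 says: "The missing category will be omitted if there are no missing values for that variable".

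**Most common TEAEs.** SAP 8.4.1 states: "Most common TEAEs reported >5% in either treatment group will also be summarized by PT". The sentence before it provides the full table: "Additionally, incidence of TEAEs will be summarized by PT". The section closes with listings, including all AEs by participant; the last item is worded "most frequent (5%) TEAEs will be provided", with no inequality sign.

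**Denominators.** Under SAP 5.2, "a sample size of approximately 40 participants with HD will be randomized in a 1:1 ratio to SAGE-718 and placebo"; Protocol 7.2 gives 20 per arm. For participants with HD, the Safety Set counts those given IP (SAP 7.2), analysed by actual treatment (SAP 8.1 and 8.4). No safety hypothesis is tested (SAP 8.4).

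**The concern.** AE incidence is a secondary endpoint. With no hypothesis tests on safety, the descriptive tables are the evidence that readers will use.

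The severity rule removes an event because one of its attributes is unknown. The table then shows neither the event nor a reason for the gap. An omitted event can lower a participant's maximum grade, or remove the participant from the row, but it cannot raise the grade. The count at or above any given grade can therefore only be too low.

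The more-than-5% rule is a percentage applied at the arm size where one participant is exactly 5%. A difference of one dosed participant decides whether a term seen once in that arm is called most common. If the arms are 19 and 20, the count that triggers inclusion differs between them.

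**Working it through.** **Arm size.** Inputs from SAP 5.2: 32 evaluable, 20% dropout, 1:1. Then 32 / (1 − 0.20) = 40, or 20 per arm, which reproduces the plan's figure.

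**1. Missing severity.** No rate of missing severity is given, so the expected size cannot be computed. The possible cases in a given row are:

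- The only event is ungraded: the participant is in the TEAE count but at no grade. In an arm of 20 this is 1/20 = 5 percentage points missing from the severity breakdown.
- The ungraded event was truly the worst, beside a graded milder one: the participant appears at the milder grade.
- The ungraded event was no worse than a graded one: nothing changes.

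No case moves a participant upwards. The first also means that the severity rows do not sum to the TEAE total.

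**2. The cut-off.** The smallest count k with k/n > 0.05:

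| Dosed in arm (n) | 1/n | k needed |
|---|---|---|
| 18 | 5.56% | 1 |
| 19 | 5.26% | 1 |
| 20 | 5.00% | 2 (10.0%) |
| 21 | 4.76% | 2 (9.5%) |

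The requirement stays at 2 up to n = 39.

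The chance that a term meets the cut-off is binomial: 1 − (1 − p)^19 for an arm of 19, and 1 − (1 − p)^20 − 20p(1 − p)^19 for an arm of 20. The rates p are assumptions, taken as equal in both arms, with the arms independent. The chance for either arm is 1 minus the product of the two chances of not meeting it.

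| True rate p | Arm of 19 | Arm of 20 | Either, 19/19 | Either, 19/20 | Either, 20/20 |
|---|---|---|---|---|---|
| 2% | 0.32 | 0.06 | 0.54 | 0.36 | 0.12 |
| 5% | 0.62 | 0.26 | 0.86 | 0.72 | 0.46 |
| 10% | 0.86 | 0.61 | 0.98 | 0.95 | 0.85 |

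With a rule of at least 2 participants in either arm, the values at p = 5% become 0.43, 0.44 and 0.46 for 19/19, 19/20 and 20/20. For an arm of 19, P(at least 2) = 1 − 0.95^19 − 19 × 0.05 × 0.95^18 = 0.245. The step is gone.

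**How unequal arms could arise.** SAP 8.2.1 provides for participants randomised but not treated. SAP 8.1 moves anyone who took any SAGE-718 to that group, so one dispensing error could turn 20/20 into 21 on SAGE-718 and 19 on placebo. A term seen once, on placebo, would then be selected; a term seen once, on SAGE-718, would not.

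**The case against.** Much of the case against a stronger reading stands.

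- A reader might infer that the TEAE tables are misstated. They are not. An ungraded event stays in the overall TEAE count, the SOC/PT table, the unrestricted PT table and the full AE listing. The cut-off only selects rows for an additional table, and a term that qualifies in one arm is selected on an either-arm basis, so no displayed rate is distorted.
- Missing severity should be rare, since Protocol 12.2.5 has the investigator report intensity for each AE.
- A reader might infer that the SAP has a worst-case convention from which severity alone departs. It does not: missing seriousness is not imputed either.
- SAP 8.1 is not a clear contradiction. The sentence before the one quoted limits when a missing category is used, and a specific rule in 8.4.1 may override a general one. Section 8.1 supports a Missing row but does not compel it.
- One extra participant does not take the 5%-rate selection chance from 0.86 to 0.46. That needs two, one in each arm; a single one takes it from 0.86 to 0.72, or from 0.72 to 0.46.
- Reading the listing's 5% as at least 5% is an inference. It may be shorthand for the table's rule.
- Any percentage cut-off has steps in small samples, and no decision in the documents depends on this table.

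What remains is that the severity rule, whenever it affects the table, does so in one direction, and that the step in the cut-off lies exactly at the planned arm size.

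**Conclusion.** The concern holds as a small improvement to two displays. The severity rule is the main part: it can understate severity and leave rows that do not reconcile, and its size is unknown because no missing rate is given. The cut-off is secondary. The step between 19 and 20 is exact arithmetic; the selection probabilities rest on the assumed rates of 2% to 10% and on final arm sizes that the documents give only approximately. The documents do not support a claim that any TEAE incidence is wrong or that a safety conclusion would change because of either rule.

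**What to change.** 1. In SAP 8.4.1, replace the omission with a Missing row in the overall, SOC and PT severity tables, without imputation. Count there each participant who has TEAEs in that row but none with a recorded grade; the rows then add up to the TEAE total. A footnote giving the number of participants with any ungraded TEAE would also cover those who have a graded event as well. Cost: SAP wording, one table row and a footnote.

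2. Define most common as reported by at least 2 participants in either arm, and use that same definition for the listing. Cost: wording only. The downside is that, with arms of 19 or fewer, single-participant terms leave the most-common table; they remain in the unrestricted PT table. If the percentage is kept, state the inequality in both places and accept the step knowingly.

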8.4.2. Clinical Lab

Clinical laboratory assessments will include blood samples for hematology, clinical chemistry, coagulations, and urinalysis. Samples will be collected ≤ 2 hours prior to dosing on dosing days. On non dosing days, collection may occur at any time.

The actual results as collected will be displayed in the listings.

All laboratory values will be summarized for the Safety Set using actual treatment received. Results of continuous hematology, clinical chemistry parameters, coagulation, and urinalysis parameters (quantitative) at each scheduled visit and mean changes from baseline will be summarized using standard international (SI) units. In addition, it will also include the summary of last post-baseline value on treatment (on or after first dose, on or before last dose) and on study (on or after first dose, on or before last day of the study).

All laboratory results will be listed in individual participant data listings.

Normal ranges for each parameter will be provided by the central laboratory. Shift from baseline to worst post-baseline values at any time on treatment, and shift from baseline to the last value on treatment (on or after first dose, on or before last dose) and the last value on study (on or after first dose, on or before last day of the study) in abnormality of results will be summarized. If a participant has both low and high post-baseline records, the participant will be counted twice for each low and high cell.

The number and percentage of participants with potentially clinically significant (PCS) values will be provided in separate displays in hematology, clinical chemistry and liver function tests provided for such occurrence for anytime on treatment, last value on treatment, after the last dose of treatment (follow-up period). PCS values will be identified for specific laboratory parameters as outlined in Table 12.

Liver function tests will be monitored closely for PCS values, and will be summarized for occurrence anytime post-baseline for the following parameters for these PCS threshold (for condition involving more than one parameter, the results need to be from the same timepoint):

- Alanine Aminotransferase: $>3\times\text{ULN}$, $>5\times\text{ULN}$, $>10\times\text{ULN}$
- Aspartate Aminotransferase: $>3\times\text{ULN}$, $>5\times\text{ULN}$, $>10\times\text{ULN}$
- Alanine Aminotransferase or Aspartate Aminotransferase: $>3\times\text{ULN}$, $>5\times\text{ULN}$, $>10\times\text{ULN}$
- Alkaline Phosphatase: $>1.5\times\text{ULN}$, $>2\times\text{ULN}$
- Total Bilirubin: $>1.5\times\text{ULN}$, $>2\times\text{ULN}$
- Total Bilirubin $>2\times\text{ULN}$ AND (Alanine Aminotransferase or Aspartate Aminotransferase $>3\times\text{ULN}$) [any time post-baseline, does not need to be measured at the same time point of assessment]
- [Total Bilirubin $>2\times\text{ULN}$ AND Alkaline Phosphatase $<2\times\text{ULN}$ (any time post-baseline, measured at the same time point of assessment)] AND [(Alanine Aminotransferase or Aspartate Aminotransferase $>3\times\text{ULN}$) AND Alkaline Phosphatase $<2\times\text{ULN}$ (any time post-baseline, measured at the same time point of assessment)]

Any lab results considered clinically significant by the investigator will be captured as adverse events, hence will show up in AE displays.

Table 12. Potentially Clinically Significant Values for Specific Laboratory Parameters

Laboratory Parameter	Sex	Units	Criteria for PCS Values (Observed values)	
			High	Low
Hematology				
Hemoglobin	Male	g/L	>185	<115
	Female	g/L	>170	<100
Hematocrit	Male	Fraction of 1	>0.55	<0.385
	Female	Fraction of 1	>0.49	<0.345
Platelet count		10 ⁹ /L	>600	<125
White blood cell		10 ⁹ /L	>15	<2.5
Basophils		10 ⁹ /L	>0.5	NA
Eosinophils		10 ⁹ /L	>1.5	NA
Neutrophils		10 ⁹ /L	NA	<1.5
Lymphocytes		10 ⁹ /L	>6.0	<0.5
Monocytes		10 ⁹ /L	>1.4	NA
Coagulation				
Prothrombin time (PT)		Sec	>=1.11 x ULN	Not Specified
Partial thromboplastin time (PTT)		Sec	>1.5 x ULN	Not Specified
Serum Chemistry				
Albumin		g/L	>70	<28
Blood urea nitrogen		mmol/L	>10.71	NA
Calcium		mmol/L	>2.75	<2.0
Chloride		mmol/L	>120	<90
Creatinine		mmol/L	>3xULN or >3x Baseline	
Gamma Glutamyl Transferase			>3xULN	
Glucose		mmol/L	>13.9	<2.8

Laboratory Parameter	Sex	Units	Criteria for PCS Values (Observed values)	
			High	Low
Sodium		mmol/L	>150	<132
Potassium		mmol/L	>5.4	<3.3
Protein		g/L		<45
Bicarbonate		mmol/L	>34	<18
Phosphorus		mmol/L	>1.94	<0.61
Liver Function Tests (LFT)				
Bilirubin		µmol/L	>2xULN	NA
Aspartate Aminotransferase		U/L	>3xULN	NA
Alanine Aminotransferase		U/L	>3xULN	NA
Alkaline Phosphatase		U/L	>1.5xULN	NA

8.4.3. 12-Lead Electrocardiogram

A single 12-lead ECG under Protocol Amendment 1 and 2 and triplicate 12-lead ECG under Original Protocol will be performed after the participant has been resting in the supine position for at least 5 minutes. If the multiple 12-lead ECG are performed, the average of all values on the same date will be used in the summary. If there are both scheduled visit and unscheduled visit on the same date, all the assessments on that date are considered as the scheduled visit for the summary. A summary of the observed values (raw values for the single ECG; average values for the multiple ECG on the same date) and change from baseline values will be summarized by each scheduled visit for the following ECG parameters: heart rate, PR, QRS, QT, and QT corrected according to Fridericia's formula (QTcF) interval. This summary will also include the last values on treatment and on study. A by-participant listing of 12 lead ECG will also be provided for each of the ECG measurements.

Each ECG is evaluated as 'normal', 'abnormal, not clinically significant' and 'abnormal, clinically significant'. The number and percentage of participants with the categories of 'abnormal, clinically significant' and 'abnormal, not clinically significant' from the latest triplicated ECG value will be provided at baseline and each post-baseline scheduled assessment time point.

Potentially clinically significant values of QTcF as outlined in Table 13 will be summarized by treatment for anytime on treatment, last value on treatment, after the last dose of treatment (follow-up period). Electrocardiogram findings will be listed by participant and visit.

Table 13. Potentially Clinically Significant Values for 12-Lead ECG Parameters

12-Lead ECG	Units	Criteria for PCS Values (Observed values)		Criteria for PCSC values (Change from Baseline)	
		High	Low	Increase	Decrease
QTcF	msec	>450 but ≤480 >480 but ≤500 >500	NA	≥30 to 60 >60	NA

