8.4. Safety Analysis

Safety and tolerability of SAGE-718 is a secondary objective of this study. The incidence of adverse events/serious adverse events, and changes in vital signs and clinical laboratory parameters are secondary endpoints, change from baseline in electrocardiograms and responses on the Columbia-Suicide Severity Rating Scale are the other endpoints (Table 8). All safety analysis will be performed on the Safety Set using actual treatment received.

The safety endpoints evaluated at scheduled visits within treatment period are taken as done in nominal visit, without any windowing. If a value is available for a nominal scheduled visit, that value will be used in summary by visit. If scheduled visit value is not available, a value from the specific visit window will be included in summary. For Post-treatment period visits, the choice of the visit will follow the same rule as described in Table 9, Table 10 and Table 11.

Anytime on treatment, last value on treatment and last value on study will be included in the summaries whenever indicated in the relevant sections below. Anytime on treatment is defined as measurement on or after first dose, on or before last dose. Last value on treatment is defined as the last post-baseline value between first dose of IP (exclusive) and up to last dose of IP (inclusive). Last value on study is defined as the last post-baseline value after the first dose of IP.

No statistical hypothesis testing will be conducted on the safety analyses.

Table 8. Summary of Safety Endpoints

Safety Evaluation	Incidence	Raw Value	Change from Baseline	Normal Range Shift from Baseline	Potentially Clinically Significant	Abnormality/ Clinical Significance
Adverse Events	X					
Clinical Laboratory		X*	X	X	X	*
Physical Exam		*				
Vital Signs		X*	X		X	
ECG		X*	X		X	*
C-SSRS		X*		X		

Safety Evaluation	Incidence	Raw Value	Change from Baseline	Normal Range Shift from Baseline	Potentially Clinically Significant	Abnormality/ Clinical Significance

ECG = Electrocardiograms; C-SSRS = Columbia–Suicide Severity Rating Scale X = value will be summarized in tables * = value will be listed in individual participant data listings
						

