8.4.4. Vital Signs

Vital signs will include oral temperature (°C), respiratory rate (breaths per minute), heart rate (beats per minute [bpm]), and blood pressures (mmHg). Heart rate and blood pressure were collected in supine position and standing position at all scheduled time points.

Vital sign results and mean changes from baseline will be summarized by scheduled visit. This will also include the summary of last values on treatment and on study assessments. Potentially clinically significant values as outlined in [Table 14](#) will be summarized by treatment and for anytime on treatment, last value on treatment, after the last dose of treatment (follow-up period). By-participant listing of vital signs will also be provided.

Table 14. Potentially Clinically Significant Values for Vital Sign Parameters

Vital Sign	Units	Criteria for PCS Values (Observed values)		Criteria for PCS values (Change from Baseline values)	
		High	Low	Increase	Decrease
Heart rate (supine and standing)	Beats/min	>120	<40	NA	NA
Respiratory Rate	Breaths/min	>20	<8	NA	NA
Systolic blood pressure (supine and standing)	mmHg	>180	<90	≥30	≥30
Diastolic blood pressure (supine and standing)	mmHg	>110	<50	≥20	≥20
Supine – Standing Systolic Blood Pressure	mmHg	≥20			

Vital Sign	Units	Criteria for PCS Values (Observed values)		Criteria for PCS values (Change from Baseline values)	
		High	Low	Increase	Decrease
Supine – Standing Diastolic Blood Pressure	mmHg	≥10			
Orthostatic hypotension: supine – standing SBP and DBP	mmHg	SBP ≥20 and DBP ≥10			
Possible orthostatic hypotension: supine – standing SBP and DBP	mmHg	SBP ≥20 or DBP ≥10			

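### Observed-value PCS counts for QTcF, laboratory tests and vital signs include participants who already met the criterion at baseline, and no baseline PCS column or PCS shift is planned

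*SAP*

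**What the plan says.** SAP sections 8.4.2 to 8.4.4 define potentially clinically significant (PCS) values mainly by fixed limits on the observed value (Tables 12, 13 and 14).

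- **QTcF (8.4.3):** "Potentially clinically significant values of QTcF as outlined in Table 13 will be summarized by treatment for anytime on treatment, last value on treatment", and after the last dose. The observed-value bands are above 450 to 480, above 480 to 500, and above 500 msec.
- **Laboratory (8.4.2):** "The number and percentage of participants with potentially clinically significant (PCS) values will be provided in separate displays", for the same three periods. The separate liver thresholds "will be summarized for occurrence anytime post-baseline for the following parameters for these PCS threshold".
- **Vital signs (8.4.4):** the same three periods apply to heart rate, blood pressure, respiratory rate and the supine-to-standing drop.

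Section 8.4 fixes the on-treatment window by date alone: "Anytime on treatment is defined as measurement on or after first dose, on or before last dose".

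Some baseline context is planned:

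- Table 13 has a change criterion for QTcF (30 to 60 and above 60 msec).
- Table 14 has change criteria for supine and standing blood pressure (systolic 30, diastolic 20 mmHg).
- The creatinine limit reads ">3xULN or >3x Baseline".
- Laboratory tests have normal-range shift tables.
- Investigator ECG categories are tabulated at baseline and at each visit.
- By-participant listings are planned throughout.

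**The concern.** A reader of an on-treatment PCS table will take each count as something that appeared on treatment. The rule counts anyone who meets the limit in the window, high or low, including anyone who met it before the first dose. Elsewhere the SAP does use baseline: a TEAE needs onset on or after first dose, or worsening, and C-SSRS categories are shown as shifts from baseline. The PCS observed-value counts have no equivalent.

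At about 20 HD participants per arm, one participant is 5 percentage points (1/20). One or two carried-over cases can visibly move a column. No safety testing is planned, so raw counts are what readers will compare.

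**Working it through.** The plan states no PCS figure to reproduce. The check has three parts.

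**1. Can a participant enter already meeting a criterion?** The only numeric vital-sign limits at entry are supine (protocol section 8.2, exclusion 6):

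| Supine measure | Allowed at entry | PCS limits (Table 14) | Baseline PCS possible? |
|---|---|---|---|
| Heart rate (bpm) | 50 to 100 | <40, >120 | No |
| Systolic (mmHg) | 100 to 160 | <90, >180 | No |
| Diastolic (mmHg) | 60 to 100 | <50, >110 | No |

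Supine heart rate and blood pressure therefore drop out of the concern. No numeric limit is set for QTcF, the Table 12 laboratory values, standing values, orthostatic drop or respiratory rate. For example, a supine systolic of 100 is allowed. A drop of 20 gives a standing value of 80, which meets both the drop criterion (20 or more) and the standing limit (below 90) before any dose.

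**2. Does the rule count such a participant, and does another display correct it?**

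- QTcF 455 at baseline, 456 on treatment: counted in the band above 450 to 480, although the change is +1 msec.
- QTcF 485 at baseline, 484 on treatment: counted in the band above 480 to 500, although the value fell.
- Neither meets the 30 msec change criterion, but that criterion is a separate column and leaves the band counts as they are.

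| Parameter | Change criterion | Shift planned (Table 8) |
|---|---|---|
| QTcF bands | Yes, separate | No |
| Standing blood pressure | Yes, separate | No |
| Standing heart rate | No | No |
| Respiratory rate | No | No |
| Supine-to-standing drop | No | No |
| Laboratory | Creatinine only | Yes, by normal range |

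For laboratory limits set as multiples of the ULN, a participant over the PCS limit at baseline is necessarily high at baseline in the shift table. The shift shows that the abnormality pre-existed, though not that it reached the PCS limit.

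ECG and laboratory tests have one scheduled on-treatment visit, Day 28 (SAP Appendix A). For them a single carried-over value can decide a participant's classification.

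**3. How large is the effect?** Inputs: 32 evaluable HD participants with 20% dropout gives 32/0.80 = 40 randomized, or 20 per arm, as in SAP section 5.2. Baseline prevalence p and persistence r on treatment are assumptions, since the documents give neither. With no drug effect, carried-over cases per arm are X1, X2 ~ independent Binomial(20, q), where q = p × r. The expected count per arm is 20q, and P(at least one in an arm) = 1 − (1 − q)^20. P(|X1 − X2| ≥ 2) is the sum of P(X1 = i)·P(X2 = j) over all i, j differing by 2 or more.

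| p | r | q | Expected per arm | P(at least 1 in an arm) | P(arms differ by 2 or more) |
|---|---|---|---|---|---|
| 1% | 100% | 0.01 | 0.2 | 0.18 | 0.028 |
| 2% | 100% | 0.02 | 0.4 | 0.33 | 0.084 |
| 5% | 50% | 0.025 | 0.5 | 0.40 | 0.115 |
| 5% | 100% | 0.05 | 1.0 | 0.64 | 0.253 |
| 10% | 80% | 0.08 | 1.6 | 0.81 | 0.365 |
| 10% | 100% | 0.10 | 2.0 | 0.88 | 0.417 |

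Worked line for p = 5%, r = 100%: P(difference 0) = 0.310 and P(difference 1) = 0.437, so P(2 or more) = 1 − 0.310 − 0.437 = 0.253. With 16 per arm, the 5% and 10% full-persistence figures become 0.201 and 0.361.

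**The case against.** **Nothing is mislabelled or hidden.** The tables head these limits as observed values, and the SAP never calls PCS counts treatment-emergent. Counting every on-treatment outlier is an inclusive convention that loses no case. This stands, and it is why the all-participant counts should remain. It does not help a reader separate new from pre-existing values.

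**Context is already planned.** Change criteria, laboratory shifts, baseline ECG categories and listings cover part of the gap. This stands for standing blood pressure and most laboratory tests. It does not reach orthostatic drop, standing heart rate or respiratory rate. For QTcF, the investigator categories are not QTcF bands and are not cross-tabulated with baseline.

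**Table shells may add a baseline column.** They are not among the documents, so this cannot be excluded. The SAP text does not ask for one.

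**A reader might infer that the comparison with placebo is biased.** The documents do not support that. Allocation is randomized 1:1, so carry-over is equal in expectation. It raises both arms and adds noise. A treatment-emergent count with the same event rate would vary by chance just as much; the gain is that what is counted is new.

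**A reader might also infer that a secondary endpoint is compromised.** That too goes beyond the text. SAP section 8.4 names AE/SAE incidence and changes in vital signs and laboratory parameters as the secondary endpoints. ECG is among the other endpoints, and PCS counts are supporting displays.

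**Conclusion.** The point holds in a limited form. As written, the observed-value PCS counts for QTcF bands, laboratory limits (high or low), standing heart rate and blood pressure, supine-to-standing drop and respiratory rate include participants who met the same criterion before dosing, and the SAP plans no display of baseline PCS status. The gap is largest for orthostatic drop, standing heart rate, respiratory rate and the QTcF bands. It is partly covered for laboratory tests and standing blood pressure. It does not affect the change-from-baseline criteria or the creatinine alternative relative to baseline.

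The size depends on how common the criterion is at entry. A chance difference of two or more participants has probability from about 3% at 1% prevalence to about 42% at 10%, with full persistence and 20 per arm. The higher figures should not be read across to rare criteria such as QTcF above 500 msec or transaminases above 3×ULN without evidence that those are common at entry. The displays are descriptive and no planned analysis becomes invalid. This is a cheap improvement.

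**What to change.** In SAP sections 8.4.2 to 8.4.4:

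1. Keep the all-participant PCS counts as they are.
2. Add a treatment-emergent PCS count: participants meeting the criterion post-baseline among those with a baseline value who did not meet it then. For QTcF, count those in a higher band than at baseline. Alternatively, cross-tabulate baseline PCS status by worst post-baseline status.
3. Do this at least for QTcF bands, orthostatic drop, standing heart rate and respiratory rate.
4. List participants whose PCS value was already present at baseline and persisted, so that none disappears from view.

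The cost is SAP wording, one extra flag per parameter and minor programming. Baseline values are already collected at screening and Day -1. The downside is a slightly smaller denominator for the treatment-emergent rows.
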